Overview of Data Sources, Data Collection Time Points, and Key Measures: The data sources, data collection time points, and key measures to achieve our specific aims are discussed by specific aim, and

summarized in Table 1 below.

Table 1: Data sources, data collection time points, and key measures by research specific aim

Data sources	Data collection time point(s)	Key Measures				
Aim 1: Effect of DWHP Support on care quality and efficiency						
Electronic medical records	Baseline & throughout implementation*	Quality of Care: Proportion of care that is guideline-adherent; Efficiency of Care: Proportion of in-person specialist visits that are preventable				
Aim 2: Impact in changing provider behavior, self-rated WH knowledge, skills, and self-efficacy						
E-consult referring provider brief survey	After each e- consult	Change in patient management for patient who is the subject of the SCAN/e-consult; change in provider knowledge				
DWHP self-assessment tool	Baseline and during implementation	DWHP self-rated WH knowledge, skills, and self-efficacy				
Aim 3: Attitudes about DWHP Support, its use, specialist time for implementation, other features						
Semi-structured interviews with DWHPs	Baseline and during implementation	Familiarity with SCAN-ECHO programs. Attitudes and beliefs regarding intervention; motivation and opportunity for its use. Familiarity with DWHP Support (reach and adoption) and other SCAN-ECHO programs; Influence of acceptability, usability, barriers and facilitators on use; Motivation and opportunity for sustained use				
Aim 4: Develop tools to measure quality of WH care in VA						
Clinical practice guidelines	To commence at start of study	Not applicable [chart abstraction templates will be produced]				

^{*}Electronic records from the baseline time periods will be assessed retrospectively

Specific Aim #1: To evaluate the effect of DWHP Support on WH care quality and efficiency using a stepped wedge design with sites participating in DWHP Support.

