We hypothesize that *DWHP Support* will improve the quality and efficiency of WH care in CBOCs. We expect that these effects may be influenced by baseline characteristics of the DWHPs (e.g., time in practice), patient conditions and characteristics, and practice characteristics, as well as DWHPs' use of the intervention. For this aim, our analytic sample will be limited to sites participating in DWHP Support outside of GLA, given that DWHP support was piloted in GLA and therefore does not have a recent "control" period (i.e., GLA was contaminated by the pilot). We will, however, use GLA data to pilot our electronic medical record (EMR) data abstraction procedures. We will also collect GLA e-consult data because this data were not contaminated by the piloting of SCAN-ECHO at GLA.

Dependent Variables: The main outcome measures will be quality of care defined by adherence to practice guidelines. We will assess quality of care and efficiency of care using the VA electronic medical records (EMR) of all female patients seen by DWHPs during the data collection period. With the modified stepped wedge design, each participating site healthcare system is contributing data to both intervention and control periods, thereby addressing comparability concerns. We expect to identify multiple episodes of care per DWHP over the combined data collection periods, where we define an episode of care as the care initiated by the DWHP for a WH condition, irrespective of whether it occurs over one or multiple encounters, and is face-to-face or not.⁵⁴

Electronic medical record (EMR) data abstraction: To assemble the relevant data from the EMR using the VHA Health Information Access (HIA) program's Data Use Agreement protocols, we will use the *Corporate Data Warehouse (CDW)*, accessed through VINCI and discussed above and, as needed, the Compensation and

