Trained chart abstractors will review each chart to complete the chart abstraction templates with the information requested. They will not be making a direct determination of care quality or efficiency, but rather obtaining the information for a computerized algorithm that will do this. A WH specialist will be available to them to answer questions that may arise. We will develop a database (using REDcap software) so that data may be entered directly into REDcap via a study computer. Senior research staff who are clinicians will randomly spot-check chart abstraction data, throughout the data collection period, to verify adherence to study protocols.

Independent Variables: *DWHP characteristics* may influence the quality and efficiency of the care that they provide, as well as their response to the intervention. We will extract DWHP characteristics from the Personnel and Accounting Integrated Data System (PAID) Master File, which contains the human resources data for all VA employees, including provider gender, age, education and licensure (MD, NP, PA), and medical specialty. We will obtain *characteristics of patients* seen by the DWHP in the study period from VA administrative data. This data will include: female caseload (# of uniques) and workload (# of encounters), female percent of total caseload and workload. We will derive percent of female workload by age category (<45, 45-64, 65+, corresponding to reproductive age group, age for emergence of chronic conditions, and older).

Aim #1 Statistical Analysis: We will calculate descriptive statistics of the proportion of CBOC women's primary care that is guideline-adherent. We will examine each of these descriptive statistics by clinical condition, and conduct z-tests for differences in proportions between conditions. We will also evaluate a series of logistic regressions to test for association of the composite measure of quality with each of the various independent variables in order to build a predictive model. Because of the hierarchical nature of the data (episode of care within patient within DWHP), a generalized linear model (GLM) approach using a logit link will be used to estimate and test the significance of the regression coefficients.

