For the analysis of the intervention effect over time, we will conduct a modified stepped-wedge analysis. This analysis takes into account the hierarchical nature of the data, with episodes of care occurring over time, and being nested within DWHPs. In the stepped wedge analysis, calendar time is divided into steps, corresponding to the time periods when providers are initially exposed to the intervention.

Sample Size and Power Calculations: The power calculations are predicated on the goal of evaluating the performance of DWHPs through the episodes of care they see. There are two levels of clustering: DWHPs within healthcare systems and episodes of care within DWHPs. We are making the assumption that there is little or no correlation between the DWHPs. As a result, we performed the calculations via the single level of clustering within DWHPs, with the episode of care as the unit of analysis. We will assume two values for the intra-cluster correlation coefficient (ICC): 0.03 and 0.05. The latter is relatively large compared to results that have been reported in the literature. The calculations assume a two-tailed 5% significance level and power of 80% to detect a difference between the study arms (with the study arm referring to intervention versus control, and including all data collection in each of those study periods, respectively). The statistical test involved is a simple z-test for the comparison of two proportions, but the actual analysis will be more sophisticated using covariates and adjusting for the actual number of episodes seen by a given DWHP. Thus, it can be assumed that the sample size calculations presented here are conservative.

With a baseline estimate from our preliminary data that 67% of episodes of care are fully proficient, then with 25 episodes of care per DWHP, we could detect small to medium effects of the intervention (see Table 2). If the baseline proficiency was 80%, then we could detect a medium size intervention effect, whereas if the baseline proficiency was 50%, we could detect a very small effect. If we increased the number of eligible episodes of care from which to measure proficiency to 50 per DWHP, then with a baseline proficiency of 67%, we could detect a small intervention effect. The number of available DWHPs (approximately 20 per study arm) and episodes of care provides us with >80% power.

Table 2: Number of DWHPs needed to detect the effects in each scenario with 80% power

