% of episodes of care with fully proficient care quality and efficiency Control Intervention (effect size)		25 episodes per DWHPper study arm* ICC=0.03 ICC=0.05		50 episodes per DWHPper study arm* ICC=0.03 ICC=0.05	
80%	90% (medium)	14	18	10	14
67%	83% (medium)	8	10	6	8
67%	77% (small)	22	28	16	22
50%	63% (very small)	16	20	12	16

^{*}study arm refers to intervention versus control, and includes all data collection

Aim #2:

We hypothesize that *DWHP Support* will increase DWHPs' practice expertise, and thereby modify their practice behavior, resulting in improved quality and efficiency (the focus of Aim 1). To test this hypothesis, we will collect process outcomes for the components of the intervention and their effects on patient care with a SCAN/e-consult referring provider survey (here after referred to as e-consult survey).

Provider Behavior: e-consult referring DWHP brief surveys: We will obtain the names of participating providers who initiate gynecology e-consults by obtaining from CDW, through VINCI, a list of all participating site gynecology e-consults. After each e-consult has been completed, we will email a request for the providers who initiated the consult to complete a brief survey about the encounter, including if and how it impacted their management plan. More specifically, we will ask: to what extent the consult altered the diagnostic, patient counseling, and/or treatment plans for this patient; the provider's confidence in their ability to implement the recommended diagnostic, patient counseling and/or treatment plans; how much, if at all, the provider learned something from the consult; and how, if at all, the consult affected the provider's plans to refer the patient for an in-person consultation. For the referring provider surveys, we will use the question about effect on the provider's plans to refer the patient to separately estimate number of avoidable consults averted by the availability of e-consults. An open-ended question, asking for additional comments, will also be included. The e-consult referring provider survey will be administered online (using Inquisite software) and responses will be confidential.

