clarity. After we make this initial revision, we will ask the nurse abstractor to use the form to abstract data from the EMRs of 10-20 patients (identified via the same process as the initial 10-20 patients, using ICD9 and CPT codes while working on the VINCI server platform), asking questions when needed and noting difficulties. We will revise the form based on this feedback and then re-test serially until all problems are resolved. We will also develop training materials for our nurse abstractors.

Creating computer programs to operationalize specifications: Finally, we will create a program, using STATA 11, to operationalize the specifications and algorithms. As needed by our if/then statements, this will include variable construction, such as converting linear variables (e.g. age) to bivariates/categorical (e.g., >30 years of age or ≤30). Then we will develop programs to operationalize the algorithms formed with the if/then statements to make a final determination of whether or not the care was guideline adherent (as a yes/no determination). For each episode of care, all relevant if/then statements must reflect the guideline-adherent action in order for that episode of care to be classified as guideline-adherent. For cases in which the program determines the care to not be adherent, the program will also specify where in the algorithm the care failed to be guideline adherent. We will test and validate this program for a sample of 25 cases in each condition, by having an investigator who is blinded to the computer determination, review the information entered into the abstraction form and determine if the care was adherent, and if not, identify where it was non-adherent. We will compare these manual determinations to those of the computer, correcting any errors in the programming that may be revealed by the discordances. The investigator will also have both the EMR chart extract and the completed chart abstraction form, to determine if all of the pertinent information is in the form to allow him/her to make an accurate decision.

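### Table 2 is labelled for an undefined joint quality-and-efficiency measure, so the claim of more than 80% power is not shown to apply to guideline adherence, and on the table's own inputs it holds only in part

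*Combined protocol and SAP*

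**What the plan says.** **Main outcome.** Dependent Variables (Aim #1) names quality of care "defined by adherence to practice guidelines". The part of Aim #4 on creating computer programs makes this a yes/no result per episode: "all relevant if/then statements must reflect the guideline-adherent action".

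**Efficiency.** Table 1 lists it as a separate Aim 1 measure: "Efficiency of Care: Proportion of in-person specialist visits that are preventable". The denominator is visits, not episodes.

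**Analysis.** Aim #1 Statistical Analysis plans "descriptive statistics of the proportion of CBOC women's primary care that is guideline-adherent" and regressions to "test for association of the composite measure of quality with each of the various independent variables". The composite is not defined and efficiency is not mentioned. The stepped-wedge paragraph names no outcome.

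**Power.** The column heading of Table 2 reads "of episodes of care with fully proficient care quality and efficiency". The text above the table says "With a baseline estimate from our preliminary data that 67% of episodes of care are fully proficient" and does not mention efficiency. It then states that the available DWHPs, about 20 per study arm, and their episodes give more than 80% power. The term *fully proficient* appears only in the power section and is not defined there.

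**The concern.** The endpoint in the heading of the power table is not the endpoint named as the main outcome. No section says how a visit-based efficiency measure would be combined with an episode-based adherence measure into one result per episode. The 67% also cannot have been produced by the scoring algorithm, because Aim #4 builds that algorithm within this study. So the plan gives no baseline, effect or ICC that is tied explicitly to guideline adherence.

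This is the plan's only power statement. If the trial shows no clear effect, readers will use the claim of more than 80% power to judge whether a worthwhile improvement in adherence was missed. They need to know which outcome and which size of effect the claim covers.

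**Working it through.** **Inputs** (Sample Size and Power Calculations; Table 2): two-sided 5% level, 80% power, z-test of two proportions, ICC 0.03 or 0.05, m = 25 or 50 episodes per DWHP, about 20 DWHPs per arm. The check accepts the plan's own simplification to two independent arms with a single level of clustering.

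**Formulas.** With p̄ = (p1 + p2)/2:

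- Episodes per arm without clustering: n = [1.96·√(2p̄(1−p̄)) + 0.842·√(p1(1−p1) + p2(1−p2))]² / (p1−p2)²
- Design effect: DE = 1 + (m−1)·ICC
- DWHPs per arm: k = n·DE/m, rounded up
- Effective n with 20 DWHPs: 20·m/DE

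**Step 1: reproduce Table 2.** For 67% to 77%, n = 316. For m = 25 and ICC 0.03, DE = 1 + 24 × 0.03 = 1.72 and k = 316 × 1.72/25 = 21.7, so 22. The other columns give 316 × 2.20/25 = 27.8 (28), 316 × 2.47/50 = 15.6 (16) and 316 × 3.45/50 = 21.8 (22). These are the printed values. Of the 16 cells, 14 match exactly. The other two differ by one through rounding (10.03 printed as 10, and 20.06 printed as 20). Only two proportions, m and the ICC enter the calculation, so it is valid for any binary per-episode endpoint with those values.

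**Step 2: power with 20 DWHPs per arm, on the table's own inputs.**

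| | m = 25, ICC 0.03 | m = 25, ICC 0.05 | m = 50, ICC 0.03 | m = 50, ICC 0.05 |
|---|---|---|---|---|
| Effective n per arm | 291 | 227 | 405 | 290 |
| 80% to 90% | 92% | 85% | 98% | 92% |
| 67% to 83% | 99% | 98% | >99% | 99% |
| 67% to 77% | 77% | 66% | 89% | 77% |
| 50% to 63% | 89% | 80% | 96% | 89% |

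The claim holds for three of the rows (one cell sits at 80%). It fails for 67% to 77% in three of four columns, whatever the endpoint is called.

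**Step 3: smallest difference detectable with 80% power and 20 DWHPs per arm** (same formula solved for p2, columns in the same order).

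| Baseline | Points | Range |
|---|---|---|
| 50% | 11.5 / 13.0 / 9.8 / 11.5 | 9.8–13.0 |
| 67% | 10.4 / 11.7 / 8.9 / 10.4 | 8.9–11.7 |
| 80% | 8.5 / 9.4 / 7.3 / 8.5 | 7.3–9.4 |

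**Step 4: what the label could mean for adherence.** If 67% is a joint rate, baseline adherence is at least 67%, but the documents do not give it. As an assumption, take independent components with adherence 80% and efficiency 84%, so that 0.80 × 0.84 = 0.672. A joint rate of 77% can then arise in different ways:

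- Both components rise: 0.857 × 0.90 = 0.771. Adherence goes from 80% to 85.7%, and power for adherence is 36–58% across the four columns.
- Efficiency stays at 84%: 0.77/0.84 = 0.917. Adherence goes from 80% to 91.7%, and power is 95–99.8%.

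Power for the joint measure is 66–89% in both cases. The same joint effect can therefore mean lower or higher power for adherence, depending on how it splits between the components.

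**The case against.** The best defence is that the heading is loose labelling. Quality and efficiency are paired throughout the Aim 1 text. The paragraph that introduces the 67% speaks only of proficiency, and no per-episode joint endpoint is constructed anywhere. On that reading *fully proficient* simply means the all-or-none adherence result, and Table 2 already is the adherence table. The table also covers control rates of 50%, 67% and 80%, and planning values often come from data older than the final instrument.

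Much of this stands. A reader might infer that the power calculation is wrong, or that it cannot apply to the main outcome. The documents do not support that: the arithmetic is correct, and the label may be no more than wording. A reader might also infer that the trial is badly underpowered for adherence, citing the 36–58% above. That figure is one end of a range set by assumed inputs, and the other end is 95–99.8%. Nor can it be said that the plan definitely never analyses a joint endpoint, since the composite is undefined and the stepped-wedge outcome is unnamed.

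The defence does not remove the gap. The heading says quality and efficiency, nothing in the plan equates *fully proficient* with guideline-adherent, and a spread of baselines does not justify the effects attached to them. It also leaves untouched the 67% to 77% row, which falls short under any label.

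**Conclusion.** The concern holds in a limited form, as two points. First, the claim of more than 80% power is not shown to apply to guideline adherence, because its inputs are labelled for an undefined joint measure and its baseline predates the scoring tool. It is unsupported rather than refuted, and no single corrected power figure can be derived from the documents.

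Second, as a blanket statement the claim is not fully met by the table itself: the 10-point effect from the 67% baseline needs more than the roughly 20 DWHPs available except with 50 episodes and ICC 0.03. This second point needs no assumption beyond the plan's own inputs and its two-arm, single-level simplification. The plan expects covariate adjustment to make its calculation conservative. That is not quantified, so it cannot be credited against the shortfall.

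**What to change.** 1. Define *fully proficient*, or replace it with guideline-adherent, in both the power text and the heading of Table 2. Name the outcome of the stepped-wedge analysis in the same terms. If a joint measure is wanted, define it per episode and give it its own row.
2. Replace the blanket power claim with the smallest detectable difference at about 20 DWHPs per arm, using the Step 3 ranges for baselines of 50%, 67% and 80%.
3. Once the retrospective control-period records have been scored with the Aim 4 algorithm, and before any intervention comparison, update the adherence baseline and ICC and restate the detectable difference.

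The cost is wording and a small recalculation. Item 3 must wait for the algorithm and for abstraction of the baseline records, which is planned but not yet done. No DWHPs, sites or procedures are added. The drawback for the sponsor is that the stated power becomes less favourable for the smaller effect.

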Intervention: DWHP Support will be comprised of two components. [1] Gynecology (Women's Health) Econsults: This is asynchronous PC consultation primarily via electronic communication; the telephone may also be used if needed. The DWHP will electronically message a gynecologist for expert guidance on WH issues that are within the scope of practice for the PC setting (i.e., medical and gynecologic in the Handbook 1330.01), but about which the DWHP needs additional guidance. The PC consultation component, adapted from the SCS's e-consult program, formalizes and allows for long-distance "curbside" consultations that are often used by PCPs in larger, multi-disciplinary settings. All e-consults will be answered within three business days. The gynecologists, who will have dedicated time protected, through clinical funds, to answer these consults, will review the patient's chart as needed, and provide an answer electronically. The DWHP is responsible for acting on the recommendations and/or submitting a request for an in-person consultation, if this is the recommendation or they are not comfortable implementing the care plan. The DWHP can also electronically ask the gynecologist clarifying or additional questions, if needed. If necessary, phone calls between the DWHP and gynecologist will be arranged. [2] SCAN-ECHO: In these monthly group interactive case consultation conferences, held via CTV, cases are submitted to the multidisciplinary team by DWHP participants, with defined clinical questions pertaining to a patient. Cases will be selected by the gynecologist based on their educational merit; those not selected will be answered electronically or by telephone (and thereby become e-consults). The gynecologist discusses the case with the patient's DWHP, with other DWHPs observing. For each session, the gynecologist also gives a 15-minute didactic related to the discussed case. Each tele-video conference thereby, in addition to providing expert consultation for the care of that patient, educates all the participating DWHPs on their care of patients with similar conditions. Participants receive continuing medical education (CME) credits for each SCAN-ECHO session.

Usual Care: Usual care in VA CBOCs includes availability of patient referral for in-person specialist consultation (typically at the parent VAMC); access to web-based tools such as *UpToDate*,⁵⁰ a clinical decision support system to which the VA subscribes; and access to monthly WH cyber-seminars.

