Because we are interested in affecting CBOC DWHP behavior—as well as knowledge, skills, and selfefficacy—it is necessary to develop an understanding of the context in which the changes are to occur and the resource needs that could impact maintenance of DWHP Support. Accordingly, our evaluation includes baseline assessment of DWHP providers, a process evaluation of the intervention, and a post-intervention assessment. We do so guided by the RE-AIM framework – a comprehensive framework designed to evaluate the impact of multilevel interventions in real-world settings.⁷⁴ RE-AIM has as a central tenet that the ultimate impact of an intervention is due to a combination of its reach, effectiveness, adoption, implementation, and maintenance. Aim 3 examines reach, adoption, and implementation of DWHP Support. Reach refers to the participation rate among those approached, which we will document. Barriers to participation (e.g., scheduling) may impact reach, and will be assessed. Adoption concerns the percentage and representativeness of settings that will conduct a given program. Adoption is impacted by several organizational factors, e.g., level of resources and expertise required, and how similar the proposed intervention is to current practices. We will measure potential variables influencing adoption of practice standards. Hypothesized effects of DWHP Support include reduced need for in-person specialty consultation, and fewer in-person visits associated with specialty consultations; therefore, we will calculate the number of SCAN/e-consults needed to avert one in-person specialist visit. Implementation refers to intervention integrity, or the quality and consistency of delivery. We will conduct a process evaluation to provide a context for the effectiveness findings, and to define resources and other factors that influence implementation.

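### As described, the ratio of consults per in-person visit averted would count referrals dropped but not referrals newly prompted, and would rest on stated plans; it needs a net definition

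*Combined protocol and SAP*

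**What the plan says.** **The survey estimate.** Aim #2 (Provider Behavior) draws its survey list from CDW as "a list of all participating site gynecology e-consults". The trigger is: "After each e-consult has been completed, we will email a request for the providers who initiated the consult to complete a brief survey". One item asks "how, if at all, the consult affected the provider's plans to refer the patient for an in-person consultation". That item will be used to "separately estimate number of avoidable consults averted by the availability of e-consults".

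**The ratio.** Aim #3, in the RE-AIM paragraph, states: "we will calculate the number of SCAN/e-consults needed to avert one in-person specialist visit". It gives no formula, data source, netting rule or interval.

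**Referral after an e-consult.** The Intervention section makes the DWHP responsible for acting on the advice and/or "submitting a request for an in-person consultation, if this is the recommendation", or if the DWHP is not comfortable carrying out the plan. The description of e-consults under Research Aims likewise lists advice to see the patient in person among the specialist's possible replies.

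**Scope.** Aim #2 names the instrument a "SCAN/e-consult referring provider survey (here after referred to as e-consult survey"), and Table 1 gives its measure as "Change in patient management for patient who is the subject of the SCAN/e-consult". The list and trigger quoted above mention e-consults only.

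**The concern.** The survey item runs in both directions: a provider can answer that the consult removed a planned referral or that it created one. The stated use keeps only the first kind. It also rests on what the provider plans just after the consult, whereas the Aim #3 ratio is expressed in visits. No check of plans against records is described.

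If the ratio is built from the only input the plan describes, it is a gross, intention-based count. Aim #3 is meant to inform sustainability and spread, and the ratio is tied there to the hypothesis of fewer in-person consultations. If the choice between gross and net is left until the data are seen, the reported efficiency could differ materially on the same responses.

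**Working it through.** The plan states no value, formula or target for the ratio, so there is no figure to reproduce. The rates below are assumptions, varied to show the range.

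**Notation**
- a = share of e-consults after which a planned in-person referral is dropped
- p = share after which a referral is newly prompted
- v = share of dropped referrals that stay dropped

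**Step 1: gross against net.** Gross ratio = 1/a. Net ratio = 1/(a − p). For 0 < p < a, 1/a < 1/(a − p), so the gross figure is the more favourable one. If p = 0 they agree. If p ≥ a, no visits are averted on balance and the net ratio has no meaning.

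| a | gross 1/a | net, p = 5% | net, p = 10% | net, p = 15% |
|---|---|---|---|---|
| 20% | 5.0 | 1/0.15 = 6.7 | 1/0.10 = 10.0 | 1/0.05 = 20.0 |
| 40% | 2.5 | 1/0.35 = 2.9 | 1/0.30 = 3.3 | 1/0.25 = 4.0 |
| 60% | 1.7 | 1/0.55 = 1.8 | 1/0.50 = 2.0 | 1/0.45 = 2.2 |

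The gap depends strongly on a: it is small at 60% and can be large at 20%.

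**Step 2: plans later reversed.** Ratio = 1/(a × v). With a = 40%, 2.5 becomes 1/(0.40 × 0.80) = 3.1 at v = 80% and 1/(0.40 × 0.60) = 4.2 at v = 60%. The direction is the same as in step 1.

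**Step 3: does the SCAN-ECHO gap push the same way?** Take 100 e-consults with 40 referrals dropped and 25 presented SCAN-ECHO cases, of which a share b drop a referral.
- Complete data: 125/(40 + 25b) = 3.1, 2.8, 2.5 and 2.3 at b = 0, 20%, 40% and 60%.
- SCAN-ECHO cases counted as consults but not surveyed: 125/40 = 3.1, which is equal to or less favourable than the complete figure.
- SCAN-ECHO cases left out of both parts: 100/40 = 2.5, which is too favourable only if b is below 40%.

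So the scope gap is neutral or unfavourable in one case and has no fixed direction in the other.

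**The case against.** **The plan does not say that newly prompted referrals are excluded.** True. A reader might infer a deliberate gross rule, but the text only leaves netting unspecified, and the item would collect what a net figure needs. Nor does the plan say that the Aim #3 ratio will use the Aim #2 estimate; that is inferred because no other input is given. Table 1 lists a record-based efficiency measure under Aim 1 (the share of in-person specialist visits judged preventable), but nothing ties it to this ratio.

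**Gross may be the intended quantity.** Aim #2 speaks of avoidable consults. A referral prompted by specialist advice may be needed, and some in-person requests after an e-consult would already have been planned. Subtracting new referrals answers a different question, about visit volume. This stands as a reason to report both figures. It does not settle which one the Aim #3 wording means.

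**Stronger readings that fail.** A reader might conclude that the ratio must come out too favourable. That holds only if some referrals are newly prompted or some dropped ones are later made. A reader might add the e-consult-only survey list as a further favourable bias; step 3 shows that it is not one, and the survey's own name and Table 1 point to SCAN-ECHO cases being included. Nor is this the main resource figure: it takes one clause, and Aim #3 also covers specialist time.

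**Records cannot replace the survey.** CDW shows referrals made, not what would have happened without the e-consult. The consult-request extraction described under Aim 1 is for tracer-condition patients, so it does not already cover every e-consult. Both points stand and limit the fix.

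**Conclusion.** The concern holds in a limited form. The ratio is undefined, and the only estimator described for it counts consults averted, from stated plans, with no allowance for referrals newly prompted. Followed as written, it is too favourable if p > 0 (with p < a) or if v < 1. At the assumed a = 40% and p = 10% the difference is 2.5 against 3.3. The true size is unknown because the documents give no rates. The conclusion rests on the inference that the Aim #2 estimate feeds the Aim #3 ratio.

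The conflict over whether presented SCAN-ECHO cases are surveyed is a separate inconsistency: it leaves the unit of the ratio unclear without biasing it in a set direction. This is a secondary descriptive measure, and the guideline-adherence outcome of Aim 1 is not affected.

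**What to change.** 1. Define the ratio on net referrals (dropped minus newly prompted) and report it beside the gross count of avoidable consults averted. Give a confidence interval clustered by DWHP. Since the ratio is unstable when the net share is near zero, form the interval for a − p and invert it only where it excludes zero.
2. As a check on plans, extend the CDW query to in-person gynecology consult requests within a fixed, pre-stated window after each listed e-consult. Say in the SAP that this shows whether dropped referrals were later made, not what would have happened without the e-consult.
3. Reconcile the survey's list and trigger with its name and Table 1. Unless presented SCAN-ECHO cases are also surveyed, state the ratio for e-consults only.

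**Cost.** SAP wording and a modest extra CDW pull, because the present extraction of consult requests is described for tracer-condition patients only. Matching a survey answer to its e-consult needs a key, and the plan describes no such linkage; it must fit the confidentiality promised to respondents. The reported figure may become less favourable. The intervention and the Aim 1 analysis do not change.
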